Color photographs (with metric ruler)				X (If positive at baseline, follow the same schedule as CT/MRI of chest, abdomen, and pelvis. Or if clinically indicated.)						
Electrocardiogram (12-Lead ECG)		X			X					
Blood sample for Capmatinib Extensive and non-Extensive PK sampling		X	X							
IRT Registration/ Treatment Dispensing/ Discontinuation				X (study treatment dispensing only)	X					

Period	Treatment					Post treatment follow-up*				
						Safety Follow-up				
	Visit Name	C3	C4	Subsequent cycles	EOT	30 day	60 day	90 day	120 day	150 day
Days	D1	D1	D1			-	-	-	-	-
Capmatinib administration	X (continuous BID dosing)									
Safety follow-up						X	X	X	X	X

 
• X = assessment to be recorded in the clinical database or received electronically from a vendor; S = assessment to be recorded in the source documentation only.
 
										
*Following the approval of protocol amendment 01, tumor assessment follow-up and survival follow-up will not be performed										

Table 8-2 Assessment Schedule - Part 2 (Randomized part) - obsolete since Part 2 will not be initiated

Period	Screening		Treatment							Post treatment follow-up										
	Visit Name	Molecular assays	Main screening	C1		C2	C3	C4	C5	C6	Subsequent cycles	EOT	Safety Follow-up					Survival Follow-up		
				30 day	60 day	90 day	120 day	150 day												
Days		-28 to -1	D1	D15	D1	D1	D1	D1	D1	D1			-	-	-	-	every 12 weeks			
Informed consent for molecular pre-screening	X																			
Confirmation of EGFR wt and ALK rearrangement negative status (local data)	X																			
Collection of archival tumor sample or newly obtained tumor sample for central MET testing (if no local data available)	X																			
Informed consent		X																		
MET mutation status (result of central testing or local data, if available)	X																			

Final

Period	Screening		Treatment								Post treatment follow-up					
	Visit Name	Molecular assay	Main screening	C1		C2	C3	C4	C5	C6	Subseque nt cycles	EOT	Safety Follow-up			
				30 day	60 day	90 day	120 day	150 day								
Days		-28 to -1		D1	D15	D1	D1	D1	D1	D1			-	-	-	-
Inclusion / Exclusion criteria		X														
Demography		X														
Smoking history		X														
Diagnosis and extent of cancer		X														
Prior antineoplastic therapy (meds, surgery, radiation)		X														
Relevant medical history/current medical conditions		X														

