**Table 8-3 Imaging Assessment Collection Plan**

Procedure	Screening/Baseline	During Treatment/Follow-up
CT or MRI of chest, abdomen and pelvis with i.v. contrast	Mandated	Mandated every 8 weeks (+/- 7 days) until at least 2 post-baseline assessments have been obtained, then every 12 weeks thereafter until PD determined by investigator assessment (with or without confirmation by BIRC) or EOT. Following the approval of protocol amendment 01, tumor assessment follow up will not be performed and study imaging will no longer be reviewed by BIRC.
CT or MRI of brain with i.v. contrast	Mandated	Mandated if positive at baseline following the same schedule as CT/MRI of chest, abdomen, and pelvis. Or if clinically indicated.
CT or MRI of other metastatic sites (e.g., neck, etc.)	Mandated if metastatic sites are suspected	If other metastatic sites are positive at baseline, follow the same schedule as CT/MRI of chest, abdomen, and pelvis. Or if clinically indicated.
Whole body bone scan*	Mandated	If clinically indicated.
Localized bone CT, MRI or X-ray	Mandated for any lesions identified on the whole body bone scan that are not visible on the CT/MRI of chest, abdomen, and pelvis or brain	If positive at baseline follow the same schedule as CT/MRI of chest, abdomen, and pelvis. Or if clinically indicated.
Color photographs with a metric ruler	Mandated if skin metastases are present.	If positive at baseline follow the same schedule as CT/MRI of chest, abdomen, and pelvis. Or if clinically indicated.

\*Whole body bone scan according to imaging vendor specifications.

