## Post-Treatment Efficacy Follow-up

Subjects who discontinue treatment for reasons other than disease progression as per RECIST 1.1 confirmed by BIRC will continue to perform tumor assessments every 8 weeks in parallel to the safety and/or survival follow-up until documented disease progression (see [Section 9.2.2](#)).

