#### **12.4.1.3 Handling of intercurrent events of primary estimand**

##### **Part 1: Single Arm run-in Part**

The primary estimand will account for the different intercurrent events as follows:

- **Discontinuation of spartalizumab for any reason:** BOR will take into account all available tumor assessments irrespective of spartalizumab discontinuation reasons.
- **Discontinuation of tumor assessment follow up with approval of protocol amendment:** BOR will take into account all available tumor assessments up to the last valid tumor assessment prior to approval of protocol amendment.
- **Any public health emergency as declared by local or regional authorities, e.g., pandemic, epidemic or natural disaster:** BOR will take into account all tumor assessments irrespective of any public health emergency.
- **New anti-neoplastic therapy:** Tumor assessment data collected after starting new anti-neoplastic therapy will be excluded from the BOR derivation.

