## Progression free survival (PFS)

The analysis in this section refer to the PFS as per local investigator assessment for Part 1.

PFS is defined as the time from the date of start of treatment (Part 1) to the date of the first documented progression according to RECIST 1.1, or death due to any cause. If a subject has no progression or death, the subject is censored at the date of last adequate tumor assessment. Definition of last adequate tumor assessment is provided in [Appendix 1](#).

PFS will be summarized using the KM method, based on FAS. Median PFS, with corresponding 95% CI, and 25th and 75th percentiles ([Brookmeyer and Crowley 1982](#), [Klein and Moeschberger 1997](#)) will be presented. KM estimates for PFS proportions at specific timepoints, along with 95% CI ([Greenwood's formula](#), [Kalbfleisch and Prentice 2002](#)) will also be provided.

Participants who did not receive one of the investigational drugs will be excluded from the PFS analysis.

PFS will be censored at the date of the last adequate tumor assessment prior to the earliest of analysis cut-off date, the start of a subsequent anti-neoplastic therapy (if any), if the event occurred after two or more missing tumor assessments, or study treatment discontinuation before radiological progression or death. Clinical progression without objective radiological evidence will not be considered as documented disease progression. The date of last adequate tumor assessment is the date of the last tumor assessment with overall lesion response of CR, PR or SD before an event or a censoring reason occurred. If no post-baseline assessments are available (before an event or a censoring reason occurred), the date of enrollment will be used.

The number of subjects censored and reasons for censoring will be summarized using descriptive statistics.

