**1.2.1 Primary estimand**

The primary scientific interest is to estimate the effect of capmatinib in combination with spartalizumab in terms of overall radiological response by investigator assessment as per RECIST 1.1 in first line NSCLC with METΔex14 mutation.

The primary estimand is characterized by the following attributes:

1. Population: adult patients with NSCLC with METΔex14 mutation in first line setting. Further details on the population are provided in Section 5 of protocol amendment 01.
2. Treatment: capmatinib in combination with spartalizumab without any new anti-neoplastic therapy. Further detail about the treatment is provided in Section 6 of protocol amendment 01.
3. Variable: Best Overall Response (BOR) defined as the best response recorded from the start of the treatment until disease progression/recurrence by investigator assessment as per RECIST 1.1
4. Intercurrent events:
  - Discontinuation of spartalizumab for any reason (treatment policy strategy)
  - Discontinuation of tumor assessment follow up with approval of protocol amendment 01 (while on treatment strategy)
  - Any public health emergency as declared by local or regional authorities, e.g., pandemic, epidemic or natural disaster (treatment policy strategy)
  - New anti-neoplastic therapy (while on treatment strategy)

Details on how to handle the intercurrent events are provided in [Section 2.5.3](#).

5. Summary measure: Proportion of subjects with a confirmed CR/PR as BOR, with its corresponding two-sided exact binomial 95% CI.

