### 2.5.3 Handling of intercurrent events for the primary estimand

The primary estimand will account for the different intercurrent events as follows:

- Discontinuation of spartalizumab for any reason:** BOR will take into account all available tumor assessments irrespective of spartalizumab discontinuation reasons.
- Discontinuation of tumor assessment follow up with approval of protocol amendment:** BOR will take into account all available tumor assessments up to the last valid tumor assessment prior to approval of protocol version 01.
- Any public health emergency as declared by local or regional authorities, e.g., pandemic, epidemic or natural disaster:** BOR will take into account all tumor assessments irrespective of any public health emergency.
- New anti-neoplastic therapy:** Tumor assessment data collected after starting new anti-neoplastic therapy will be excluded from the BOR derivation.

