#### **Progression free survival (PFS)**

PFS is defined as the time from the date of start of treatment to the date of the first documented progression according to RECIST 1.1, or death due to any cause. Clinical deterioration without objective radiological evidence will not be considered as documented disease progression.

PFS will be summarized using the KM method, based on FAS. Median PFS, with corresponding 95% CI, and 25th and 75th percentiles ([Brookmeyer and Crowley 1982](#), [Klein and Moeschberger 1997](#)) will be presented. KM estimates for PFS proportions at specific timepoints (3, 6, 9, 12, and 18

months), along with 95% CI (Greenwood's formula, [Kalbfleisch and Prentice 2002](#)) will also be provided. The number (%) of events and subjects censored will also be summarized.

Participants who had never received one of the investigational drugs will be excluded from the PFS analysis.

PFS will be censored at the date of the last adequate tumor assessment prior to the earliest of analysis cut-off date, the start of a subsequent anti-neoplastic therapy (if any), if the event occurred after two or more missing tumor assessments, or study treatment discontinuation before radiological progression or death (for patients who discontinued study treatment before radiological progression/death and also prior to the approval of protocol version 01, PFS will be censored at the date of the last adequate tumor assessment prior to the approval of protocol version 01). The date of last adequate tumor assessment is the date of the last tumor assessment with overall lesion response of CR, PR or SD before an event or a censoring reason occurred. If no post-baseline assessments are available (before an event or a censoring reason occurred), the date of enrollment will be used. If a subject has no progression or death, the subject is censored at the date of last adequate tumor assessment.

The number of subjects censored and reasons for censoring will be summarized using descriptive statistics.

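### The BOR cut-off at approval of amendment 01 is not limited to subjects already in post-treatment tumor follow-up, so read literally it could drop on-treatment scans from the primary ORR

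*SAP*

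**What the plan says.** ORR by investigator assessment is the only primary endpoint of Part 1. It counts confirmed CR or PR only, and it is estimated with an exact interval, not tested.

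SAP 1.2.1 lists as one intercurrent event "Discontinuation of tumor assessment follow up with approval of protocol amendment 01 (while on treatment strategy"). SAP 2.5.3 turns this into a derivation rule: "BOR will take into account all available tumor assessments up to the last valid tumor assessment prior to approval of protocol version 01". Protocol 12.4.1.3 reads almost identically: "BOR will take into account all available tumor assessments up to the last valid tumor assessment prior to approval of protocol amendment". Neither sentence mentions whether the subject is still on treatment.

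For PFS, SAP 2.7.1 also uses the approval date, but only "for patients who discontinued study treatment before radiological progression/death and also prior to the approval of protocol version 01". The protocol's PFS text (12.5.2.1) has no approval date; among its censoring reasons it lists "or study treatment discontinuation before radiological progression or death". So the SAP added the clause for PFS and left the BOR sentence as it was.

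The protocol describes what the amendment stopped. The footnote to Table 8-1b says: "Following the approval of protocol amendment 01, tumor assessment follow-up and survival follow-up will not be performed". Table 8-3 has "Following the approval of protocol amendment 01, tumor assessment follow up will not be performed". Before the amendment, under Post-Treatment Efficacy Follow-up in 8.3.1.3, subjects who left treatment without BIRC-confirmed progression "will continue to perform tumor assessments every 8 weeks in parallel to the safety and/or survival follow-up until documented disease progression".

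Scans on treatment continue. Table 8-1b, Table 8-3 and section 8.3.1.2 keep them every 8 weeks until two post-baseline assessments exist and every 12 weeks after that, to progression or end of treatment. Section 9.2.1 asks for two post-baseline assessments in subjects who received spartalizumab before any transfer, so that the primary outcome can be completed.

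**The concern.** The sentence that will be programmed for the primary endpoint is broader than the event it is meant to handle. Applied as written, it discards scans that the amended protocol still collects, some of them expressly for the primary outcome. SAP 2.5.4 then makes this matter: a CR or PR with no later assessment to confirm it counts as a non-response. A subject with a first PR before approval and the confirming scan after it would move from responder to non-responder through wording alone.

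The direction is fixed. Removing later scans can undo a confirmed response but cannot create one, so ORR can only fall. DCR is derived from the same BOR but is less exposed, because under Appendix 1 (16.1.3.1) an unconfirmed PR more than 6 weeks after treatment start still qualifies as SD.

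**Working it through.** **The plan's own figures.** SAP Table 3-1 requires at least 17 responses in 30. The binomial tail, the sum over x = 17 to 30 of C(30,x) p^x (1-p)^(30-x), is 0.5025, 0.7145 and 0.9165 at p = 0.55, 0.60 and 0.67, which agrees with 50.2%, 71.5% and 91.7%. The exact 95% interval for 17/30 is 37.4 to 74.5, as stated. Neither document gives a figure that depends on the BOR cut, so the rest is a reading of the text plus a check on dates.

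**Three ways to read the bullet.**
- *Narrow:* it applies only to subjects off both drugs and in tumor follow-up at approval. Their scans stop at approval anyway, so no on-treatment scan is lost. This fits every scan provision listed above.
- *Intermediate:* it also applies to a subject on capmatinib at approval who later stops without progression. That subject too gets no tumor follow-up because of the amendment, and on-treatment scans between approval and end of treatment are lost.
- *Literal:* the sentence applies to everyone, and all on-treatment scans after approval are lost.

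The last two conflict with on-treatment scanning to progression or end of treatment, with the purpose given in 9.2.1 and with the while-on-treatment label.

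**Loss per response.** Per the Study Update in the amendment, 28 subjects received both drugs and 3 started capmatinib alone. SAP 2.5.2 excludes those who never received one of the drugs, so the denominator is 28. One lost response costs 1/28 = 3.57, or 3.6 points.

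**Dates.** The approval date is not given. The SAP Introduction gives only the release date, 13-Oct-2021, and protocol 14.1 requires approval by the sponsor, Health Authorities where required and the IRB/IEC. The dates below are therefore assumptions, and 13-Oct-2021 is the earliest possible one. Combination subjects were first dosed by 28-Jul-2021. Take a first response at week 8 confirmed at week 16 (112 days, window 7 days either way). A subject is exposed if first dosed between approval minus 112 days and 28-Jul-2021, counted inclusively:

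| Assumed approval | Exposed starts (scheduled day) | Days exposed (window) |
|---|---|---|
| 13-Oct-2021 | 23-Jun to 28-Jul | 36 (29 to 43) |
| 01-Nov-2021 | 12-Jul to 28-Jul | 17 (10 to 24) |
| 18-Nov-2021 | none | 0 (0 to 7) |
| 25-Nov-2021 | none | 0 (0) |

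For the last possible start, week 16 is 28-Jul-2021 + 112 days = 17-Nov-2021. If the first response came at week 16, scheduled confirmation would be at week 24 (28-Jul-2021 + 168 = 12-Jan-2022) or, on the 12-weekly schedule, at week 28 (28-Jul-2021 + 196 = 09-Feb-2022), so exposure would last longer. Section 8.3.1.2 allows confirmation off schedule from 4 weeks, which reduces all of these.

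**Illustration of scale.** Start from 19/28, the earlier first-line monotherapy result in protocol 1.1.1.2 and not a result of this study. Losing 0, 1 or 2 responses gives 67.9% (47.6 to 84.1), 64.3% (44.1 to 81.4) or 60.7% (40.6 to 78.5), with exact 95% intervals.

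**The case against.** The strongest reply is that the bullet is conditional by structure. Each sentence in SAP 2.5.3 handles the event in its own heading, and this heading concerns tumor assessment follow-up, which is a post-treatment phase. The amendment rationale says that such follow-up after treatment discontinuation will no longer be collected, and the list of changes places its removal under section 9.2.2, Post treatment follow-up. A subject on capmatinib at approval had no follow-up to discontinue. This argument stands as to intent: the narrow reading is the likely one.

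The PFS comparison should also not be pressed too far. The clause there sits in a parenthesis attached to censoring at treatment discontinuation, and it lets subjects who stopped early keep their follow-up scans up to approval. BOR has no matching censoring rule in SAP 2.5. The comparison shows that the authors named the affected group for PFS; it does not show that a limit was deliberately left out for BOR. Nor does the first bullet of 2.5.3 contradict the second: it says only that stopping spartalizumab does not itself restrict scans.

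What the reply does not supply is the missing condition. The programming specifications named in the SAP Introduction may contain it, but they are not among the documents, and the rule for the only primary endpoint should not depend on them.

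A reader might infer that 16 to 19 of 28 subjects are at risk, since 19 were on capmatinib on 06-Sep-2021 and 0 to 3 of those had never received spartalizumab. The documents do not support that as a measure of effect. It includes subjects whose response was already confirmed, those who never responded and those who stopped before approval. On the intermediate reading it also includes those who did not later stop without progression.

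**Conclusion.** The concern holds as a defect of wording. The BOR sentence in SAP 2.5.3 and protocol 12.4.1.3 lacks the limit that its heading and the scan schedule imply. Programmed literally, it would exclude required on-treatment scans and could turn a response confirmed after approval into a non-response.

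The cost is 3.6 points of ORR per lost response, always downward, assuming a denominator of 28. The number lost depends on start dates, response dates and an approval date that the documents do not give, and it may be zero. It would be wrong to conclude that the plan intends to drop on-treatment scans or that ORR will be biased; the text supports only that it could be. Because ORR is estimated and not tested, no formal decision turns on it. It should be corrected because it governs the only primary endpoint and the remedy is small. Confidence is medium, since the separate specifications may already apply the narrow reading.

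**What to change.** Amend the second bullet of SAP 2.5.3 before database lock, or by addendum after it, as the SAP Introduction provides. Suggested text:

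*For subjects who had discontinued study treatment (both drugs) and were in post-treatment tumor follow-up at approval of protocol version 01, BOR uses assessments up to the last valid one before approval. For subjects still receiving capmatinib at approval, the approval date does not limit BOR; on-treatment assessments count until progression or new anti-neoplastic therapy.*

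The words on both drugs are needed because SAP 2.1.1.1 defines study treatment as the combination and spartalizumab had already been stopped in all ongoing subjects. State one definition of the approval date and use it for both BOR and PFS. No other BOR rule needs to change for this correction, including the 30-day default in Appendix 1.

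The cost is one bullet and one date definition, with no new visits, scans or patient data. Protocol 12.4.1.3 can be aligned when the protocol is next amended, since a change there alone would need the approvals in section 14.1.

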### 2.5.4 Handling of missing values/censoring/discontinuations

Subjects in the FAS with unknown BOR will be noted as such in the appropriate tables/listings and counted as non-responders in the ORR calculation.

If there is no baseline tumor assessment, all post-baseline overall lesion responses are expected to be ‘Unknown’. If no valid post-baseline tumor assessments are available, the best overall response must be “Unknown” unless progression or death is reported.

If any new anti-neoplastic therapy is taken while on study any subsequent assessments will be excluded from the BOR derivation.

Subjects without confirmed CR/PR, due to lack of subsequent tumor assessment after one CR/PR, will be considered as non-responders.

## **2.5.5 Supportive and supplementary analysis**

A sensitivity analysis may be performed where subjects without a valid post-baseline assessment (unless PD or death is reported before that time) are excluded from the calculation of the ORR.

As a supportive analysis, the change in tumor size will be describe using a waterfall plot presenting the best percentage change from baseline in the sum of diameters of all target lesions.

## **2.6 Analysis of the key secondary objective**

Not applicable.

## **2.7 Analysis of secondary efficacy objective(s)**

### **2.7.1 Secondary endpoints**

The secondary efficacy endpoints are disease control rate (DCR) and progression free survival (PFS) by investigator assessment as per RECIST 1.1.

#### **Disease control rate (DCR)**

DCR is defined as the proportion of subjects with a confirmed best overall response (BOR) of complete response (CR), partial response (PR), stable disease (SD), and non-CR/non-PD (for subjects without target lesions) according to RECIST 1.1 (see [\[Appendix 16.1.1-Protocol-Section 16.1\]](#)).

DCR is calculated based on the data from the FAS and the corresponding 95% CI based on the exact binomial distribution ([Clopper and Pearson 1934](#)) will be presented.

Participants who had never received one of the investigational drugs will be excluded from the DCR analysis.

